cardiopulmonary bypass strategy based on blood gases and operative documents.

Inclusion Criteria:

• Age less than 30 days of age at time of surgery with need for cardiopulmonary bypass with

cardioplegic arrest (with or without deep hypothermic circulatory arrest)

• Diagnosis with cyanosis at baseline (pre-operative PaO2 of less than 50mmHG) due to:

o Complete admixture lesion (example: hypoplastic left heart syndrome, total anomalous

pulmonary venous return, truncus arteriosus, pulmonary atresia with VSD)

o Transposition physiology (example: D-Transposition of the great arteries or Double

outlet right ventricle with subpulmonary VSD)

o Right-to-left shunt (example: Tetralogy of Fallot, double outlet right ventricle with

suboaortic VSD and pulmonary stenosis)

Exclusion Criteria:

• Corrected gestation at time of surgery less than 37 weeks

• Prior cardiac arrest

• Current or prior history of ECMO support

• Current or prior history of needing renal replacement therapy with dialysis

• Prior cardiac surgery requiring cardiopulmonary bypass

• Diagnosis of Ebstein's Anomaly

• Known genetic syndrome other than Trisomy 21 or DiGeorge Syndrome

ProtocolVersion: 1.4 Date: 03122021

7

Subject Availability:

Based on historical data, the number of patients that fit the inclusion criteria would be about 40-50 patients

per year in this single center study. A sample size of 21 patients per treatment group (42 total patients) will

be enrolled. With a 50-67% consent rate, the study duration will be approximately 24 months.

Trial Enrollment and Randomization:

Infants will be randomized into two groups:

1. Normoxia Group (with controlled re-oxygenation):

a. Goal PaO2 on cardiopulmonary bypass of 60-100 mm Hg using lower FiO2 (blended

sweep gas) via oxygenator

b. Post-bypass, goal of PaO2 < 100 mm Hg by anesthesia and in ICU via oxygen titration via

mechanical ventilator for 24 hours post-op.

2. Standard of Care Group: Current standard of care

Randomization will be performed in random permuted block sizes of 2 or 4 and stratified by "Stage I

Palliation" (Norwood arch reconstruction with shunt placement [Right ventricle-to-pulmonary artery shunt,

modified Blalock-Taussig shunt, or central aortopulmonary shunt]) in each treatment group. Patients

undergoing Stage I palliation are known to have higher rates of complications and mortality at baseline and

therefore the stratification will be done to control for this in the randomization.

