lactate measurements will be used to verify appropriate oxygen delivery.

"Standard of Care" Group: As cardiopulmonary bypass is being weaned, anesthesia will initiate mechanical

ventilation per standard protocols. Ventilation will be continued in the ICU and adjusted per standard goals

per the intensivist.

5. Post-Operative Course:

After transfer to the PCTU from the OR, the goals as stated above based on the patient's physiology will

be maintained for 24 hours after the surgery per the goals per group and physiology.

After cardiac surgery, the following tests and evaluation will be performed:

1. At 2, 6, and 24 hours after surgery (time marked as decannulation from cardiopulmonary

biomarkers for oxidative stress, inflammation, vascular injury, neurologic,

myocardial, and renal injury will be drawn.

2. At 24, 48, and 72 hours after surgery: renal function and liver function panels will be obtained

3. A head ultrasound will be performed at 24 and 72 hours after surgery

4. EEG monitoring may be connected to each infant after arrival to the ICU as part of the standard

of care.

6. Adverse Event Assessment

Assessment of Serious Adverse Events will be performed 1month post surgery. A chart review will be

performed by the study team. If a chart review can't be accomplished, the study team will contact the patient

[figure not shown]
via phone call for an assessment. See Serious Adverse Event section of the protocol for specific definitions.

10

Date: 03122021

ProtocolVersion: 1.4

Figure 2: Study protocol flow chart

Outcomes and Analysis:

Analysis will be performed on the basis of the intent-to-treat principle. Baseline characteristics will be compared between the treatment groups using standard univariate tests.

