Specific Aim 1: The primary outcome for this aim will be systemic oxidative stress based on thiobarbituric acid reactive substances (TBARS), a measurement of lipid peroxidation, assessed at three separate time points in the first 24 hours after surgery. An analysis of co-variance will be used incorporating all available data to model the outcome with an adjustment for pre-operative baseline (although we anticipate no differences in baseline values by treatment arm due to randomization). The model will compare the mean values (and 95% confidence intervals) between the two groups at each time-point. In this model, we will assume missing data are missing at random, i.e., missing values may depend on observed but not unobserved data. Analysis will be performed on the basis of the intent-to-treat principle and will include an interim analysis after 24 patients are enrolled. In secondary analyses, we will use propensity scores to

account for any characteristics that were not balanced by treatment arm after randomization. We plan to

analyze other biomarkers of oxidative stress and organ injury using analogous analysis of variance models.

Specific Aim 2: To evaluate safety, we will assess the rate of observed adverse events between groups using

Chi-square test or Fisher's exact test as appropriate. Safety will also closely be monitored on a routine basis

by the Data Safety and Monitoring Board (DSMB). .

Specific Aim 3: To investigate optimal endpoints in the study of the clinical impact of normoxia. We will

assess clinical endpoints that may be reflective of a reduction in oxidative stress, including post-operative

length of stay, days alive and out of the intensive care unit (ICU) at 30 days after surgery, a composite

outcome of major adverse events as described above, and a global rank score. For all endpoints, data on

distribution within our study population and between the two groups will be calculated to understand effect

sizes and aid in planning subsequent studies.

1. Post-operative length of stay: Calculated as number of days in the hospital after surgery. May be an

attractive outcome as it can incorporate many of the morbidities that would be influenced by strategies to

reduce oxidative stress as most would lead to prolonged length of stay. The disadvantages are that it does

not incorporate mortality, and may be influenced by other center care processes and practices.

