a. Incidence of arrhythmias requiring medical therapy

13

ŀ

- b. VIS score on admission, 2, 6, and 24 hours post-operatively
- c. Measurement of arteriovenous saturation difference:
 - Regional venous saturation measurements (NIRS), which are routinely collected in all patients (measurements will be recorded at 2, 6 and 24 hours after surgery)
 - ii. Pulse oximetry measurements and arterial oxygen saturation (via arterial blood gas) at 2, 6, and 24 hours after surgery
- d. Lactic acid production (highest and lowest value in 12-hour increments in the first 48 hours after surgery). Arterial blood gases are routinely obtained in the post-operative period
- e. Need for stress dose hydrocortisone in the post-operative setting
- f. Biomarkers: troponin release, vascular injury (ANGPT2) and inflammatory balance (IL-6, IL-10)

4. Kidneys:

- a. % above dry-weight daily for the first 5 post-operative days (Dry weight will be defined as dosing weight which will likely be the birth weight of the infant)
- b. Days to dry weight
- c. Serum creatinine levels (comparison of pre-op, daily trends in the first 3 days including identification of peak level)
- d. Biomarkers: NGAL (urine)

5. Oxidative stress:

- a. Whole blood redox potential
- b. Biomarkers (protein carbonyls, total antioxidant capacity (TAC), and 8-isoprostanes)

6. GI:

a. Liver function tests and intestinal fatty acid binding protein (I-FABP (pre-operatively, 24, 48, and 72 hours post-operatively)

b. Time to goal feeds

Table 3: Schedule of Evaluations

^{***} Can be run with already collected samples per SOC

Test	Pre-op (within 24hrs prior to surgery)	Baseline (in OR prior to bypass)	End Rewarming	2 hour post	6 hour post	24 hour post	Morning of POD 1	Morning of POD 2	Morning of POD3	General Post-Op for 48 hours	1 month Post- op
Blood **	0 mL	2.75 mL	2.25 mL	2.75 mL	2.75 mL	2.75 mL	0 mL	0 mL	0 mL		
Renal Function Panel	X SOC						X SOC	X SOC	X SOC		
Liver Function Panel ***	X R						X R	X R	X R		
TBARS		X R	X R	X R	X R	X R					
Protein Carbonyl		X R	X R	X R	X R	X R					
8-isoprostane		X R	X R	X R	X R	X R					
Total Antioxidant Capacity		X R	X R	X R	X R	X R					
Redox Potential		X R	X R	X R	X R	X R					
i-FABP		X R		X R	X R	X R					
Troponin		X R		X R	X R	X R					
GFAP		X R	X R			X R					
Tau		X R		X R	X R	X R					
ANGPT-2		X R		X R	X R	X R					
IL-6		X R		X R	X R	X R					
II-10		X R		X R	X R	X R					
Urine		***		***							
Urine: NGAL		X R		X R							
Neuroimaging and Testing											

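### Exploratory creatinine (Kidneys, item c) is compared raw, without the daily weights in item a; if the arms differed in retained fluid, the wetter arm would read a few percent low on day 1

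*Combined protocol and SAP*

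**What the plan says.** All references are to the combined protocol and SAP.

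- **Creatinine.** Other Secondary Exploratory Outcomes, 4. Kidneys, item c: "Serum creatinine levels (comparison of pre-op, daily trends in the first 3 days including identification of peak level". These exploratory outcomes are to be compared between the two arms.
- **Fluid.** Item a of the same list records the percentage "above dry-weight daily for the first 5 post-operative days", and item b the days to dry weight. The reference weight is defined thus: "Dry weight will be defined as dosing weight which will likely be the birth weight of the infant".
- **Timing.** Post-Operative Course, item 2: "At 24, 48, and 72 hours after surgery: renal function and liver function panels will be obtained". Table 3 instead gives the mornings of post-operative days (POD) 1, 2 and 3.
- **Other kidney marker.** Table 3 schedules urine NGAL after surgery only at 2 h. Post-Operative Course, item 1, has markers of "myocardial, and renal injury will be drawn" at 2, 6 and 24 h. On either reading, creatinine is the only biochemical kidney outcome named after 24 h.
- **Model.** No model is named for creatinine itself. The nearest text, under Specific Aim 1, is the plan to "analyze other biomarkers of oxidative stress and organ injury using analogous analysis of variance models". The TBARS model it refers to adjusts only for the pre-operative baseline. Propensity scores are to "account for any characteristics that were not balanced by treatment arm after randomization".
- **Stratum.** Randomization is stratified by Stage I palliation because of its higher baseline risk: "therefore the stratification will be done to control for this in the randomization". No analysis model names the stratum.

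No text links item c to item a.

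**The concern.** If one arm retains more water, the same amount of creatinine is spread through a larger volume, and the measured value falls until production refills it. A between-arm difference in raw creatinine then mixes kidney function with dilution. It could hide a modest renal signal in the wetter arm, or suggest a small one that is not there.

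Fluid gain arises after randomization, so adjusting for the pre-operative baseline does not address it, and the propensity analysis is not stated to cover it. Items a and b would show a fluid difference, but the plan does not say how creatinine should then be read. Choosing a correction after seeing the weights would leave room to prefer one result over the other.

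Separately, leaving the Stage I stratum out of the creatinine model gives up precision that a stratified design makes available.

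**Working it through.** The documents give no figure for creatinine, fluid gain, body water or half-life, so there is no stated result to reproduce. The only document inputs are 21 infants per arm and the draw times (24, 48 and 72 h, or the mornings of POD 1-3, taken here as 18, 42 and 66 h).

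**Assumptions.** Fluid gains of 5% against 10%, and 5% against 15%, of weight; body water w = 0.70-0.80 of weight; pre-operative creatinine half-life h = 12-48 h; equal clearance in the arms; fluid gained at one time.

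**1. Ceiling (full dilution, no refilling).** With f = 1 + gain/w, the shortfall is 1 - f(dry)/f(wet). At w = 0.75:
- 5% against 10%: 1 - 1.067/1.133 = 5.9%.
- 5% against 15%: 1 - 1.067/1.200 = 11.1%.

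Over w = 0.80 to 0.70 the ceilings run from 5.6% to 6.3% and from 10.5% to 11.8%. At w = 0.60 they would be 7.1% and 13.3%.

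**2. Shortfall at the draw.** With constant production and clearance, C(t)/C0 = 1 - (1 - 1/f) exp(-ln2 · t/(h·f)).

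Example, w = 0.75, h = 24, t = 18: a 5% gain gives 1 - 0.0625 × 0.614 = 0.9616. A 10% gain gives 1 - 0.1176 × 0.632 = 0.9256. The ratio is 0.963, so the wetter arm reads 3.7% low.

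Shortfall at w = 0.75 over h = 12-48 h:

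| Draw | 5% against 10% | 5% against 15% |
|---|---|---|
| 18 h | 2.4-4.7% | 4.8-9.0% |
| 24 h | 1.8-4.3% | 3.6-8.3% |
| 66 h | 0.2-2.6% | 0.5-5.1% |

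With poor clearance (h = 96 h) the 66 h shortfall is still 3.9% and 7.5%. If fluid accumulates evenly over 24 h instead, the 24 h shortfall is 3.3-5.0% and 6.4-9.5%.

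**3. Against sampling error.** SE of the log difference = sqrt(ln(1 + CV²)) × sqrt(2/21). An assumed CV of 25% gives 0.246 × 0.309 = 0.076; a CV of 50% gives 0.472 × 0.309 = 0.146. The largest 18 h shortfall, 9.0%, is -ln(0.910) = 0.094, or about 1.2 SE at the smaller CV. For 5% against 10% the largest is -ln(0.953) = 0.048, or about 0.6 SE.

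**4. Effect on a test.** Simulated trials used 21 per arm, assumed log-SD 0.3, baseline-adjusted log creatinine and two-sided 5%. With identical kidneys, raw creatinine at 18 h is significant in 6-9% of trials (5% against 10%) or 9-21% (5% against 15%). For a true 20% rise in the wetter arm, power falls from 57-59% with equal gains to 36-47% at 5% against 10%.

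**5. What a correction does.** Multiplying creatinine by f changes the ratio by f(wet)/f(dry), which is 1.0625 or 1.125. In the example, 0.963 × 1.0625 = 1.023, now 2.3% high. Over h = 12-48 h the corrected value over-reads in the wetter arm at 18 h by 1.3-3.7% or 2.4-7.1%. At 66 h it over-reads by 3.5-6.0% or 6.8-11.9%. If fluid is lost between 24 and 48 h (h = 12), raw and corrected both read high at 48 h, by 3.0% or 6.0%.

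**6. Reference weight.** An infant 10% above birth weight from growth alone would be corrected by 1 + 0.10/0.75 = 1.133, that is, 13% too high.

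**7. Stratum.** In a simulation with equal gains and an assumed 0.3 log-unit Stage I effect, adding the stratum to the model raised power from 44% to 58%.

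**The case against.** The strongest reply is that this is not a defect. The intervention is an oxygen target, and the documents describe no path from it to fluid balance. The outcome is one line in an exploratory list of a 42-infant pilot, with no renal claim attached. Fluid will be reported by arm beside creatinine, and nothing prevents a dilution analysis later. The day-1 bias is modest against sampling error, and for 5% against 10% the false-positive rate at log-SD 0.3 is close to nominal.

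Most of this stands and sets the weight of the point. What remains is narrower: both measurements are already planned, and a reading fixed in advance is worth more than one chosen after the weights are known.

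A reader might infer that the creatinine comparison is biased as planned. The documents do not support that, because the bias exists only if fluid gains differ.

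A reader might also infer that corrected creatinine should replace raw, or that a renal conclusion should require both to agree. Neither holds up. Used alone, the correction over-reads, increasingly so by day 3. Requiring agreement recovers no masked difference: power for a true 20% rise in the wetter arm stays at 36-47%, the same as raw (18 h, 5% against 10%). When the wetter arm truly has the lower creatinine (ratio 0.83), it cuts power from 70-78% to 41-53%. With equal gains it still loses about 3-5 points. Once fluid is being lost, the two values no longer bracket the truth.

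**Conclusion.** The point holds as a minor, conditional one. The plan compares raw creatinine and does not say how to read it if the arms differ in retained fluid. Under the illustrative gains, the wetter arm would read low by at most about 6% or 12%, and by about 2-5% or 4-9% at the first draw, mostly fading by day 3 unless clearance is poor.

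The gains, body water, half-life and creatinine spread are all assumptions from outside the documents. A lower body-water fraction, or fluid still accumulating at the draw, moves the figures up somewhat.

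Nothing here supports doubt about the primary TBARS outcome, the adverse-event comparison or the composite of major adverse events, none of which uses creatinine.

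**What to change.** Before analysis, add a short paragraph to Kidneys, item c:

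- Keep raw creatinine, including the raw peak, as the reported outcome.
- For POD 1 only, add a sensitivity analysis: creatinine × (1 + fractional weight gain / body water), with body water 0.75 and checks at 0.70 and 0.80.
- Take the gain from the pre-operative weight if it is recorded. Item a's dosing weight is likely birth weight, which mixes growth or early weight loss with fluid.
- Report both estimates with confidence intervals beside the between-arm fluid difference from item a. Apply no rule that both must agree, no correction on POD 2-3 and no corrected peak.
- Fit the creatinine model with pre-operative creatinine and the Stage I stratum as covariates.

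The cost is a paragraph and one formula; creatinine and daily weights are already planned. There are two downsides. The corrected value over-reads in the wetter arm (about 1-4% at 18 h for 5% against 10%), so it should be presented as a sensitivity result and not as the true level. A pre-operative weight is also not listed among the pre-operative studies or in Table 3, so the sponsor should confirm that it is available. The stratum term costs one degree of freedom; its gain depends on how strongly Stage I status predicts creatinine.

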APPENDIX A: Acronym List

ANGPT2: Angiopoietin2

CPB: Cardio-Pulmonary Bypass

CT: Computed Tomography

ECMO: Extracorporeal membrane oxygenation

EEG: Electroencephalogram

EF: Ejection Fraction

FiO2: Fraction of Inspired Oxygen

GFAP: Glial fibrillary acidic protein

GI: Gastro-Intestinal

ICU: Intensive Care Unit

I-FABP: Intestinal fatty-acid binding protein

IL: Interleukin

IQR: Interval Quartile Range

MRI: Magnetic Resonance Imaging

NIRS: Near-infrared spectroscopy

PaO2: Partial Pressure of Oxygen

PCTU: Pediatric Cardiothoracic Intensive Care

PFT: Pulmonary Function Test

POD: Post-Operative Day

TBARS: Thiobarbituric Acid Reactive Substance

VIS: Vasoactive-Inotropic Score

VSD: Ventricular Septal Defect
